8.3.2. Method of Detecting AEs and SAEs

Care will be taken not to introduce bias when detecting AEs and/or SAEs. Open-ended and nonleading verbal questioning of the participant is the preferred method to inquire about AE occurrences.

8.3.3. Follow-up of AEs and SAEs

After the initial AE/SAE report, the investigator is required to proactively follow each participant at subsequent visits/contacts. All SAEs and AEs of special interest (AESI) as defined in Section 8.3.6 will be followed until resolution, stabilization, the event is otherwise explained, or the participant is lost to follow-up (as defined in Section 7.3). Further information on follow-up procedures is provided in Section 10.4.3.

8.3.4. Regulatory Reporting Requirements for SAEs

- Prompt notification by the investigator to the sponsor of an SAE is essential so that legal obligations and ethical responsibilities toward the safety of participants and the safety of a study intervention under clinical investigation are met.
- The sponsor has a legal responsibility to notify both the local regulatory authority and other regulatory agencies about the safety of a study intervention under clinical investigation. The sponsor will comply with country-specific regulatory requirements relating to safety reporting to the regulatory authority, IRB/IEC, and investigators.
- An investigator who receives an investigator safety report describing an SAE or other specific safety information (eg, summary or listing of SAEs) from the sponsor will review and then file it along with the IB and will notify the IRB/IEC, if appropriate according to local requirements.
- The sponsor (or its designee) will be responsible for reporting suspected unexpected serious adverse reactions (SUSARs) to the relevant regulatory authorities and the IEC/IRB as per applicable regulatory requirements. The sponsor (or its designee) will also be responsible to forward SUSAR reports to all investigators involved in the study, who will also be required to report these SUSARs to their respective IECs/IRBs, as per their local regulatory requirements.

8.3.5. Pregnancy

- Details of all pregnancies in female participants will be collected after the start of study intervention and until 90 days after the last dose of the study IMP.
- Attempts will be made to obtain details of all pregnancies in female partners of male participants that occurred after the start of study intervention and until 90 days after the last dose of IMP. Female partners will be asked to sign a relevant ICF.
- If a pregnancy is reported, the investigator will record pregnancy information on the appropriate form and submit it to the sponsor within 24 hours of learning of the female participant or female partner of male participant (after obtaining the necessary signed informed consent from the female partner) pregnancy.
- While pregnancy itself is not considered to be an AE or SAE, any pregnancy complication or elective termination of a pregnancy for medical reasons will be reported as an AE or SAE.

Clinical Study Protocol ARGX-113-2001 v2.0 Efgartigimod IV and SC

- Abnormal pregnancy outcomes (eg, spontaneous abortion, fetal death, stillbirth, congenital anomalies, ectopic pregnancy) are considered SAEs and will be reported as such.
- The pregnant participant will be followed to determine the outcome of the pregnancy. The investigator will collect follow-up information on the participant and the neonate and the information will be forwarded to the sponsor.
- If a female partner of a male participant consents, the female partner will be followed to determine the outcome of the pregnancy. In this case, the investigator will collect follow-up information on the female partner and the neonate and the information will be forwarded to the sponsor.
- Any post-study pregnancy-related SAE considered reasonably related to the study intervention by the investigator will be reported to the sponsor as described in Section 8.3.4. While the investigator is not obligated to actively seek this information in former study participants or pregnant female partners of former male study participants, he/she may learn of an SAE through spontaneous reporting.
- Any female participant who becomes pregnant while participating in the study will be discontinued from the study intervention and will continue with all remaining visits, including the EoS visit.

8.3.6. Adverse Events of Special Interest

An AESI is an event of scientific and medical concern specific to the sponsor's product or program (eg, an underlying condition being investigated, a mechanism of action/potential immunosuppression). An AESI can be serious or nonserious and related or unrelated to study IMP or procedures. Further characterizing information will be collected in the eCRF.

Efgartigimod treatment induces reductions in the IgG levels and there is a potential risk for infections associated with low IgG levels. As such, any infections are considered AESIs in this study. Further information to be collected in the eCRF will include:

- Location of the infection
- Relationship to the underlying condition, medical history, and concomitant medications
- Reoccurrence of previous infection
- Previous rescue therapy
- Any confirmatory procedure, culture, or urgent medical intervention

8.4. Pharmacokinetics

• Blood samples for pharmacokinetics (PK) will be collected from each participant as specified in the SoA (Section 1.3). Concentrations of efgartigimod will be determined using a validated method.

- Instructions for the collection and handling of biological samples will be provided by the sponsor. The actual date and time (24-hour clock time) of each sample will be recorded.
- Samples collected for analyses of efgartigimod concentration may also be used to evaluate safety or efficacy aspects related to concerns arising during or after the study.
- At visits during which blood samples for the determination of multiple aspects of efgartigimod will be taken, 1 sample of sufficient volume can be used.
- For the efgartigimod IV treatment arm, PK sampling will be performed both predose (within 1 hour prior to the start of the infusion) and postdose (within 1 hour after the end of the infusion) on dosing days. For the efgartigimod PH20 SC treatment arm, PK sampling will only be done predose (within 1 hour prior to the injection) on dosing days.
- The following PK parameters will be measured: C_{max} of efgartigimod (after all doses for the IV treatment arm) and C_{trough} of efgartigimod in both arms.

8.5. Genetics and/or Pharmacogenomics

Genetics are not evaluated in this study.

8.6. Biomarkers

See Section 8.1.1 for assessments of total IgG levels, IgG subtype levels, and AChR-Ab levels.

8.7. Immunogenicity Assessments

See Section 8.2.9 for immunogenicity assessments.

8.8. Medical Resource Utilization and Health Economics

Medical resource utilization and health economics data including ER visits, hospitalizations, and ICU admissions for any reason from 12 months prior to screening will be collected as medical history. All hospitalizations, ER visits, and ICU admissions will be collected during the study and analyzed, even if they are not classified as AEs, to compare medical resource utilization before and after efgartigimod treatment. These data will also be collected in the extension study ARGX-113-2002.

8.9. Storage of Blood Samples After the Study

Any samples remaining after the laboratory analyses defined in the protocol have been completed may be stored for up to 15 years after the end of the study for additional medical, academic, or scientific research to address any scientific questions related to efgartigimod, FcRn biology, or gMG. The samples may be stored in the laboratory or long-term storage designated by the sponsor or research partners worldwide. The storage and future use of samples obtained during this study is permitted unless local regulations do not allow it or if the participant did not consent.

In addition, blood samples may be used to validate methods to measure efgartigimod, antibodies, and biomarkers.

9. STATISTICAL CONSIDERATIONS

The statistical analysis will be performed by the sponsor's designated CRO using statistical analysis systems (SAS) software (SAS Institute, Cary, NC, United States) version 9.4 or higher, and the software package R, if applicable. The standard operating procedures (SOPs) and work instructions of the sponsor's designated CRO will be used as the default methodology if not otherwise specified.

A detailed and comprehensive Statistical Analysis Plan (SAP) will be written and signed-off prior to final analysis database lock. Minor changes to the statistical methods set out in this protocol do not require a protocol amendment but will be documented (as changes from the protocol) in the SAP and in the clinical study report(s). The below sections contain the main general features of the statistical analysis. More details will be provided in the SAP.

9.1. Statistical Hypotheses

The confirmation of the noninferiority (NI) of efgartigimod PH20 SC with efgartigimod IV will be based on the total IgG percent reduction at day 29 utilizing a noninferiority margin of 10. See Section 9.2 for justification of the noninferiority margin. The hypotheses for the evaluation of noninferiority are as follows:

- Null hypothesis: the difference in percent reduction from baseline of total IgG at day 29 for the SC treatment arm as compared to the IV treatment arm will be ≥10 (ie, µ_{IV} µ_{SC} ≥10)
- Alternate hypothesis: the difference in percent reduction from baseline of total IgG at day 29 for the SC treatment arm as compared to the IV treatment arm will be <10 (ie, µIV µSC <10)

9.2. Sample Size Determination

[figure not shown]
The noninferiority (NI) evaluation will be based on the percent reduction from baseline in total IgG levels at day 29.

To evaluate the relationship between changes in total IgG and MG-ADL, statistical modeling on MG-ADL change from study baseline with total IgG percent reduction from study baseline as a predictor and participant as a random effect was performed among all study ARGX-113-1704 participants on the efgartigimod IV 10 mg/kg treatment arm in the modified intention-to-treat (mITT) analysis set. Data from all cycles in the study were included. To minimize potential modeling bias introduced by outlier data points, only week 1 to week 6 data were included and data after week 6 were excluded. The modeling results demonstrate that total IgG percent change from study baseline and MG-ADL change from study baseline were highly correlated (p-value <0.0001) as illustrated in Figure 2. With a difference of 10 in the mean total IgG percent reduction (eg, from total IgG percent reduction of 63 to total IgG percent reduction of 53) the mean difference in MG-ADL improvement (ie, decrease from baseline) is expected to be 0.35 (2-sided 95% confidence interval, 0.236 to 0.465). In the phase 3 study ARGX-113-1704, the mean of MG-ADL improvement at week 4 of cycle 1 was 4.5 (standard error 0.36) in the efgartigimod treatment group and 2.0 (standard error 0.27) in the placebo treatment arm, which translates to a treatment effect of 2.5 (2-sided 95% confidence interval, 1.62 to 3.38). The corresponding mean of total IgG percent reduction at week 4 of cycle 1 was 62.2 (standard error

Clinical Study Protocol ARGX-113-2001 v2.0 Efgartigimod IV and SC

0.82) in the efgartigimod treatment arm and 0.1 (standard error 2.23) in the placebo treatment arm, which translates to a treatment effect of 62.1 (2-sided 95% confidence interval, 57.44 to 66.76). With a NI margin of 10 in IgG percent reduction, 84% ($1-10/62.2 \times 100\%$) of the PD effect as assessed by total IgG reduction is expected to be preserved, whereas 86% ($1-0.35/2.5 \times 100\%$) of the clinical effect as assessed by MG-ADL change is expected to be preserved.

Figure 2: Statistical Modeling on MG-ADL Change From Baseline With IgG Percent Reduction From Baseline as a Predictor and Patient as a Random Effect in All Efgartigimod IV Treated Patients in Study ARGX-113-1704 (mITT Analysis Set)

IgG= immunoglobulin G; IV=intravenous(ly); MG-ADL=Myasthenia Gravis Activities of Daily Living; mITT=modified intention-to-treat

Note: To minimize potential modeling bias introduced by outlier data points, only week 1 to week 6 data from all cycles in study ARGX-113-1704 were included.

Based on data from the phase 3 study ARGX-113-1704, the mean percent decrease in total IgG levels with the IV formulation is expected to be approximately 62 (standard deviation 7.5). Assuming the total IgG percent reduction from baseline with the SC formulation is 60 (2 less compared to the IV formulation) along with a standard deviation of 7.5, 20 participants per treatment arm are needed to reach 90% power to detect noninferiority using a 1-sided 2-sample t-test at a 2.5% level of significance. To account for participant discontinuation, 3 additional participants per treatment arm have been added. A sample size of 46 participants will need to be enrolled and randomized, allowing for a 13% attrition rate.

Clinical Study Protocol ARGX-113-2001 v2.0 Efgartigimod IV and SC

The assumptions utilized in the sample size calculations will be evaluated in study ARGX-113-1907, which will compare the PD, PK, safety, and tolerability of multiple doses of efgartigimod PH20 SC and efgartigimod IV in healthy participants. Study ARGX-113-1907 will use the same dosage as in the current study and will provide a detailed assessment of the PD effect in healthy participants, which is expected to represent the effect in participants with gMG. If the results of study ARGX-113-1907 indicate that the pooled standard deviation of the mean percent decrease in total IgG levels is larger than 7.5, the sample size will be adapted accordingly. If the pooled standard deviation is:

- 8.5, then a total of 50 participants will be recruited, with 6 additional participants added to account for discontinuations for a total of 56 participants (based on a pooled standard deviation of 8.5)
- 10.0, then a total of 68 participants will be recruited, with 8 additional participants added to account for discontinuations for a total of 76 participants (based on a pooled standard deviation of 10)

Seventy-six participants would suffice for the noninferiority comparison between SC and IV based on IgG reduction at day 29; however, increasing the sample size to approximately 110 participants will provide better quantification of the clinical safety and efficacy profile of the SC formulation in patients with gMG while the IV formulation will serve as a reference treatment in this randomized study.

Note: "Enrolled" means a participant's, or their legally acceptable representative's, agreement to participate in a clinical study following completion of the informed consent process and screening. Potential participants who are screened to determine eligibility for the study, but do not participate in the study, are not considered enrolled unless otherwise specified by the protocol. "Randomized" means that an enrolled participant has been randomly assigned to a treatment arm.

9.3. Analysis Sets

The following analysis sets are defined:

Table 2:Analysis Sets

Analysis Sets	Description
Safety analysis set	All randomized participants who are exposed to the IMP
Intention-to-treat set	All randomized participants with a value for total IgG levels at baseline and at least 1 post-baseline timepoint
PK analysis set	Subset of safety analysis set with at least 1 postdose PK measurement

9.4. Statistical Analyses

The SAP will be finalized before database lock and will include a more technical and detailed description of the statistical analyses described in this section. This section is a summary of the

planned statistical analyses of the most important endpoints including primary and key secondary endpoints.

9.4.1. General Considerations

- The baseline value will be defined as the last assessment prior to the first administration of efgartigimod.
- All study visits will be recalculated based on actual dates and will be referred to as "analysis visits," which will be used in the statistical analyses. The rules for calculating the analysis visits will be documented in the SAP. Rules for inputting partial dates or missing dates will also be documented in the SAP.

9.4.2. Primary Endpoint

Definition of the Estimand for the Primary Endpoint

- Population: intention-to-treat (ITT) analysis set (see Table 2)
- Variable: Percent reduction from baseline in total IgG levels at day 29
- Main intercurrent events:
 - early treatment discontinuation for any reason prior to day 29
 - initiation of Ig therapy (IVIg and SCIg) as rescue therapy prior to day 29
 - missed doses

Handling of Main Intercurrent Events

For early treatment discontinuation or missed doses, the observation captured 7 days after the last dose will be used. If Ig therapy is used as rescue therapy prior to day 29, the last observation prior to the initiation of Ig therapy will be used.

Estimation of Treatment Effect and Statistical Inference

An analysis of covariance model (ANCOVA) will be used to estimate the mean percent reduction in total IgG levels from baseline at day 29 for each treatment arm, as well as the 2-sided 95% confidence interval for the difference between the 2 treatment arms. The model will include treatment as a factor and baseline total IgG level as a covariate.

When the upper limit of the 95% confidence interval (mean percent reduction with IV – mean percent reduction with SC) is below the margin of 10, the SC formulation will be considered noninferior to the IV formulation.

Complementary Analyses

To facilitate interpretation of the estimated treatment effect in the primary analysis, sensitivity analyses will be conducted where the main intercurrent events will be handled differently. Details will be provided in the SAP.

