6.8.3. Prohibited Medication and Procedures

Participants must discontinue from the study intervention if any prohibited therapies are used.

During the study, participants may NOT receive:

- any monoclonal antibody
- other experimental/study IMP
- live or live-attenuated vaccines
- a change in the dose or frequency of their current gMG medication
- a change in concomitant therapy for gMG
- PLEX, IVIg, immunoadsorption, or a change in dosage or type of corticosteroid used as a monotherapy or in combination

PLEX, Ig therapy (IVIg and SCIg), immunoadsorption, or a change in dosage or type of corticosteroid are considered rescue therapy if both of the following conditions apply:

- 1. The treating physician believes that the participant's health is in jeopardy if rescue therapy is not provided, and
- 2. The participant is deteriorating clinically according to the protocol-defined criteria, which includes at least 1 of the following:
 - a. new or worsening of respiratory/bulbar symptoms, or
 - b. at least a 2-point increase in any individual nonocular items on the MG-ADL scale as compared to the previous visit

The date and time of rescue medication administration, as well as the name, dosage regimen, and response to the rescue medication will be recorded in the eCRF.

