7.1. Discontinuation of Study Intervention

Administration of the IMP may be withheld if, in the opinion of the investigator, it could put the participant at undue risk. If the IMP is being withheld and it cannot be administered during the scheduled time window, then that dose of IMP must be missed. The subsequent scheduled dose of IMP can be administered to the participant at the next scheduled treatment period (TP) visit if the investigator determines that the undue risk has been resolved. The participant may continue with the study even if they miss multiple doses.

It may be necessary for a participant to permanently discontinue study intervention.

Participants must discontinue the study intervention if:

- It is in the participant's best interest; discussion with the sponsor's medical director is encouraged prior to discontinuation
- The participant receives prohibited medication (Section 6.8.3)
- A severe hypersensitivity reaction to the IMP occurs
- The participant is pregnant
- The sponsor requests discontinuation (eg, following DSMB advice, see Section 10.1.5.1)

If study intervention is permanently discontinued, the participant will remain in the study and will complete all scheduled visits and the EoS visit on day 71 (\pm 3 days), even though the participant will not receive any more doses of the IMP. See the SoA (Section 1.3) for data to be collected at the EoS visit.

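### Minor: the pre-rescue IgG rule in Protocol 9.4.2 covers only Ig therapy, so rescue PLEX or immunoadsorption can be counted as drug effect on the primary endpoint

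*Protocol*

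**What the plan says.** Protocol 9.4.2 defines the primary variable as the percent reduction from baseline in total IgG at day 29. Three events are listed as the main intercurrent ones. The first is stopping treatment early, worded as "early treatment discontinuation for any reason prior to day 29". The second is the only one that concerns rescue, and it reads "initiation of Ig therapy (IVIg and SCIg) as rescue therapy prior to day 29". The third is doses that were missed.

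It then gives two handling rules:

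- **7-day rule:** "For early treatment discontinuation or missed doses, the observation captured 7 days after the last dose will be used".
- **Ig rule:** if rescue is Ig therapy, "the last observation prior to the initiation of Ig therapy will be used".

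Protocol 6.8.3 has a wider list of rescue: "PLEX, Ig therapy (IVIg and SCIg), immunoadsorption, or a change in dosage or type of corticosteroid are considered rescue therapy", subject to two clinical conditions. The same section states: "Participants must discontinue from the study intervention if any prohibited therapies are used". Section 7.1 repeats this and keeps discontinued participants in the study for all scheduled visits. Under the Schedule of Activities, pharmacodynamic samples are taken predose on days 1, 8, 15 and 22, then on day 29, and they may also be taken at unscheduled visits.

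**The concern.** The endpoint is total IgG itself. Giving immunoglobulin raises it; exchanging plasma or adsorbing immunoglobulin lowers it. Section 9.4.2 protects the endpoint against the first kind of contamination, which would understate the drug effect. It leaves the second kind in place, which would overstate it.

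Elsewhere the protocol treats the two alike. Section 6.8.3 groups them as rescue, and exclusion criteria 8c and 8d apply the same 4-week limit to prior Ig and prior PLEX.

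At stake is the only confirmatory comparison. A post-procedure value credits the assigned arm with IgG removal that efgartigimod did not cause. In the SC arm that favours noninferiority; in the IV arm it works against it; in either arm it adds variance. A corticosteroid change is also rescue under 6.8.3, but it does not remove IgG in this direct way and is not part of the point.

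**Working it through.** **1. Which sample is selected.** Doses fall on nominal days 1, 8, 15 and 22, IgG samples on days 1, 8, 15, 22 and 29, and no dose follows rescue. Visit windows are ignored.

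| Procedure on day | Last dose | Sample used now | Last scheduled sample before procedure |
|---|---|---|---|
| 2-7 | 1 | 8 (post-procedure) | 1 (baseline) |
| 9-14 | 8 | 15 (post-procedure) | 8 |
| 16-21 | 15 | 22 (post-procedure) | 15 |
| 23-28 | 22 | 29 (post-procedure) | 22 |
| 8, 15 or 22, after the sample, dose withheld | 7 days earlier | same day, clean | same day |

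The two choices differ on 4 × 6 = 24 of the 27 nominal days from 2 to 28. Example: dose on day 15, PLEX on day 18, value taken on day 22.

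**2. The plan's own figure.** Inputs from 9.1 and 9.2: margin 10, assumed difference 2, SD 7.5, one-sided 2.5%, 90% power. The noncentral t distribution gives 20 per arm (power 0.908), as stated. SD 8.5 and SD 10 give 25 and 34 per arm, matching the stated totals of 50 and 68. With about 110 randomized 1:1, or 55 per arm, power at difference 2 is 0.9998 (SD 7.5) or 0.986 (SD 10), before attrition.

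**3. Size of one case.** Let x be the percent reduction the drug alone would show and f the fraction of remaining IgG that the procedure has removed, net, by the time of the sample. The recorded value is x + (100 − x)·f. The documents do not give f; I assume 0.25 to 0.65. At the planned SC mean x = 60:

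- f = 0.25: gain 40 × 0.25 = 10 points; 10/55 = 0.18 points of arm mean.
- f = 0.65: gain 40 × 0.65 = 26 points; 26/55 = 0.47 points of arm mean.

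The gain is larger where x is lower, as after early rescue.

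**4. Effect on the expected difference.** The IV mean is 62. At a true difference of 10 the SC mean is 52, and with case rates p_IV and p_SC:

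observed difference = 10 + f·(38·p_IV − 48·p_SC).

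- 5% in each arm, f = 0.65: 10 + 0.65 × (1.90 − 2.40) = 9.675.
- 2% IV and 4% SC, f = 0.65: 10 + 0.65 × (0.76 − 1.92) = 9.246.
- 2% IV and 4% SC, f = 0.25: 10 + 0.25 × (−1.16) = 9.71.

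Equal rates are therefore not quite neutral: the arm with the smaller reduction has more IgG left to remove. At difference 2 (SC mean 60), 5% in each arm and f = 0.65 gives 2 + 0.65 × (1.90 − 2.00) = 1.935. The power loss there comes from added variance.

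**5. Simulation.** 200,000 trials per cell, 55 per arm, normal values, the gain in step 3 applied to each affected draw, two-sample t-test, noninferior if the upper 95% limit of IV − SC is below 10. Ranges run over f = 0.25 to 0.65.

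| Case rates | Error at 10, SD 7.5 | Error at 10, SD 10 | Power at 2, SD 7.5 | Power at 2, SD 10 |
|---|---|---|---|---|
| none | 0.025 | 0.025 | 0.9998 | 0.986 |
| 1% each arm | 0.026 | 0.026-0.027 | over 0.999 | 0.982-0.986 |
| 2% each arm | 0.027-0.029 | 0.026-0.027 | 0.999 or more | 0.977-0.985 |
| 5% each arm | 0.030-0.034 | 0.029-0.033 | 0.995 or more | 0.962-0.984 |
| 2% IV, 4% SC | 0.039-0.058 | 0.035-0.051 | over 0.999 | 0.985-0.988 |

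The reverse imbalance (4% IV, 2% SC) lowers power at difference 2 to no less than about 0.95.

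**The case against.** **The SAP may settle it.** Section 9.4.2 lists main intercurrent events only, 9.4 calls itself a summary, and Section 9 lets minor method changes be made in the SAP. That lowers the weight and cost of the point. It does not remove it: the two handling rules are already written, and read literally the 7-day rule covers these procedures and selects the wrong value. The explicit deferral to the SAP within 9.4.2 concerns the complementary analyses.

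**The Ig rule has its own cost.** With PLEX on day 18, the day 15 predose sample contains nothing of the third dose, so an upward bias gives way to a downward one. This stands. It is the compromise the protocol already accepts for Ig rescue, and it does not credit the drug with what the procedure removed.

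**It will be rare, and sensitivity analyses are planned.** This also stands. Rescue needs two conditions, both arms receive active drug, and 9.4.2 says that "sensitivity analyses will be conducted where the main intercurrent events will be handled differently".

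A reader might infer more than the documents support:

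- *That the two rules contradict each other for Ig rescue.* Ig rescue is also discontinuation for any reason, and no order is written down. But the Ig sentence is specific and unconditional, and would matter only after the fourth dose if the general rule prevailed. The natural reading is that it governs. A sentence on precedence is a clarification.
- *That rescue in the first week is recorded as a 0% reduction.* That requires baseline to count as an eligible observation, which 9.4.2 does not say. The intention-to-treat set requires a post-baseline IgG value, and unscheduled samples are possible.
- *That the noninferiority conclusion is in danger.* The raised error rates need a true difference of exactly 10, and the larger ones also need more cases in the SC arm. The protocol assumes a difference of 2 and predicts no SC excess.

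**Conclusion.** The point holds as a minor one. Section 9.4.2 states a rule that, for two of the rescue therapies named in 6.8.3, can select a post-procedure IgG value and count it as drug effect on the sole confirmatory endpoint.

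Under the assumed ranges, power at the planned difference stays at about 0.96 or more with equal rates. Error at a true difference of 10 is about 0.025-0.034 with equal rates and about 0.035-0.058 with 2% IV and 4% SC.

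These figures rest on assumed case rates and net removal, on values drawn from the planned day 29 distribution, on no attrition, and on a two-sample t-test in place of the planned ANCOVA. They show scale and are not forecasts. The textual gap does not depend on them.

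**What to change.** In Protocol 9.4.2, widen the rescue intercurrent event to the start, before day 29, of Ig therapy (IVIg or SCIg), PLEX or immunoadsorption as rescue. Use the last IgG observation before the first of these. Add, for clarity, that this rule takes precedence over the 7-days-after-last-dose rule. Carry the same text into the SAP.

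The cost is two or three sentences. No new data are needed: 6.8.3 already requires the date and time of rescue in the eCRF. No clinical rule changes, and the sample size is unaffected.

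The downside is that a pre-rescue value from an earlier visit may understate the day 29 reduction, as under the present Ig rule. For rescue before the first post-baseline sample, the handling can be varied in the sensitivity analyses already planned.

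### Section 9.4.2 reverts to a pre-Ig value only when Ig therapy counts as rescue, so other Ig use before day 29 can leave infused IgG in the primary endpoint

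*Protocol*

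**What the plan says.** Protocol section 9.4.2 lists three main intercurrent events before day 29: early treatment discontinuation, missed doses, and "initiation of Ig therapy (IVIg and SCIg) as rescue therapy prior to day 29". It gives two handling rules:

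- When treatment stops early or a dose is missed, the analysis takes the IgG sample drawn a week after the most recent administration.
- For rescue Ig the rule is: "If Ig therapy is used as rescue therapy prior to day 29, the last observation prior to the initiation of Ig therapy will be used".

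Section 6.8.3 defines rescue. Ig therapy and the other listed treatments "are considered rescue therapy if both of the following conditions apply". The first condition is a judgement: "The treating physician believes that the participant's health is in jeopardy if rescue therapy is not provided". The second is "The participant is deteriorating clinically according to the protocol-defined criteria", met by new or worse respiratory or bulbar symptoms or by a rise of at least 2 points in a nonocular MG-ADL item since the previous visit.

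The same section's list of prohibited treatments includes "PLEX, IVIg, immunoadsorption, or a change in dosage or type of corticosteroid used as a monotherapy or in combination". It names IVIg but not SCIg. On consequences it says "Participants must discontinue from the study intervention if any prohibited therapies are used". Section 7.1 keeps such participants in the study for all remaining visits, so their IgG continues to be sampled.

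**The concern.** Infused IgG raises measured total IgG whatever the reason for giving it. The protocol accepts this for rescue Ig by going back to the last value before it. Making that step depend on the indication has no measurement rationale.

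Ig given for a non-MG reason, or for MG worsening that misses the 6.8.3 criteria, is left to rules written for a different purpose. A contaminated value understates the drug's reduction. In the SC arm that enlarges the IV minus SC difference and works against noninferiority; in the IV arm it shrinks the difference and works towards it.

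**Working it through.** **Background figures.** The sample size in section 9.2 reproduces and is not in question. With margin 10, true difference 2 and one-sided 2.5%, the exact t calculation gives 20 per arm at SD 7.5 (power 0.908) and 34 per arm at SD 10 (power 0.902), as stated. About 110 randomized 1:1 is 55 per arm, with power 0.986 at SD 10.

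**Which sample is used.** Doses fall on days 1, 8, 15 and 22. Under section 1.3, IgG is sampled predose on those days and again on day 29. For Ig that is not rescue:

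| Ig starts | Last dose | Rule that applies | Sample used | Sample relative to Ig |
|---|---|---|---|---|
| Day 18 (IVIg) | Day 15 | 7 days after last dose | Day 22 | 4 days after |
| Day 25 | Day 22, all four given | None of the listed events | Day 29 | 4 days after |
| After the 7-day sample, next dose withheld or missed | 7 or more days earlier | 7 days after last dose | Drawn before Ig | Before |

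With no dose missed, an Ig start between two doses, or between the fourth dose and day 29, always precedes the sample used. Only the third row is safe.

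**SCIg.** SCIg for gMG would be a change in concomitant gMG therapy, which 6.8.3 prohibits. SCIg for another reason is not on the prohibited list, and 6.8.2 permits standard therapies for concurrent conditions unless listed. That use triggers neither handling rule, so the day-29 value stands.

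**Size, as an illustration.** The shift in an arm mean is (expected reduction − recorded reduction) / n. The expected 62 is from section 9.2, n = 55, and the recorded 0 to 40 is an assumption.

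- One participant: (62 − 40)/55 = 0.40 and (62 − 0)/55 = 1.13 points.
- Two in the same arm: 0.80 and 2.25 points.
- With the SC mean of 60 assumed in 9.2, one participant gives 20/55 = 0.36 to 60/55 = 1.09 points.

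The answer depends heavily on the assumption. If X is residual infused IgG at the sample and B is baseline IgG, the shift per participant is 100 × X/B. Taking X from 2 to 15 g/L and B from 6 to 15 g/L (only the 6 g/L entry limit is in the protocol), this runs from 100 × 2/15 = 13 to 100 × 15/6 = 250 points. Divided by 55, that is 0.24 to 4.5 points in the arm mean.

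**What a pre-Ig value would be.** It is not a full-effect value. Ig on day 18 leads back to day 15, after two doses. Ig on day 25 leads back to day 22, after three. Ig on day 3 leads back to baseline, a reduction of 0%. The protocol gives no expected reductions at these times, so the net gain from the change cannot be calculated. Within the 0 to 40% illustration, 0.4 to 1.1 points is its upper bound, and for very early Ig there may be no gain.

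**The case against.** The strongest objection is that this belongs in the SAP. Section 9.4.2 lists only the main intercurrent events, section 9.4 calls itself a summary, and alternative handling is left to sensitivity analyses in the SAP. That does not remove the point. What is deferred is the sensitivity handling; the primary rule, with its rescue condition, is fixed in the protocol.

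The second objection is that the case is nearly closed off, and most of this stands. IVIg is prohibited, the second rescue condition is broad enough to catch most serious MG worsening, and patients with IgG below 6 g/L or uncontrolled infection at screening are excluded. No section provides for Ig replacement because of low IgG. What remains is uncommon use within four weeks.

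A reader might also infer three stronger things that the documents do not support:

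- That every non-rescue Ig course contaminates the endpoint, always by way of forced discontinuation. Ig started after the 7-day sample does not contaminate it, and the discontinuation route is explicit for IVIg only.
- That a corrected rule would restore a value near 62%. It substitutes an earlier, partly treated value.
- That the open-label design produces a directional bias through how Ig is labelled. The first rescue condition is a judgement made with the arm known, but the second uses stated criteria, and nothing indicates that labelling would differ by arm.

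**Conclusion.** The point holds as a gap in a stated rule. For Ig that fails the 6.8.3 definition and starts before the sample that 9.4.2 selects, the primary value includes infused IgG. The consequence is probably small: roughly 0.4 to 1.1 points per affected participant in an arm mean, if the recorded reduction is 0 to 40% rather than 62%. Frequency and size are assumptions, and larger values are arithmetically possible. Nothing here shows an error in the test, the margin or the sample size, and the documents do not support a claim that the noninferiority conclusion is at risk. It is an optional but worthwhile clarification.

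**What to change.** In section 9.4.2, remove the rescue condition from both the intercurrent event and its handling rule. For any Ig given for any reason before day 29, use the last total IgG value before the first Ig dose. State that this takes precedence over the discontinuation and missed-dose rule whenever the 7-day sample follows Ig.

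Sections 6.8.3 and 9.4.2 should also be reconciled on SCIg, which the rescue definition and the estimand name but the prohibited list does not. How that is settled clinically is for the sponsor.

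The cost is a phrase and one precedence sentence. Section 6.8 already requires all medication to be recorded with reason and dates, so no new data are needed and the sample size is unchanged. The downside is that early Ig use yields an early value that understates the reduction, as the existing rescue rule already does.
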